Mini-Markers Scale (MM; Saucier, 1994): The Mini-Markers Scale is a 40-item self-report measure of the five factor model personality factors: extraversion, agreeableness, conscientiousness, emotional stability, and openness. It asks participants to rate how accurately each item describes themselves on a 1-9 point Likert scale ranging from "extremely inaccurate" to "extremely accurate."

Adverse Events Form: This self-report form will be administered at Visits 2 and 3 after nasal spray administration to assess for any adverse events. Participants will be asked to report on a symptom checklist whether they experienced a negative reaction to the oxytocin and placebo nasal sprays. If participants endorse 'yes' on any item, a study clinician or nurse will follow up and ask them whether the symptom resolves by the end of the study visit.

Assessment of Blind Form: This questionnaire will be given at Visits 2 and 3 after nasal spray administration to assess for participants' expectancies regarding the drug they received. Participants will be asked which nasal spray they believe they received (oxytocin or placebo), to rate their degree of certainty, and to describe their reasons why.

Tasks:

The following tasks will be administered at each study visit approximately 45 minutes after drug administration. The order of tasks will be the same within each participant in the study between Visit 2 and Visit 3 in order to minimize variance for the within-subject analysis and isolate the effect of the drug. However, the order of tasks will be counterbalanced between participants in the study, to account for possible carry-over effects.

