Posner Task (Posner, 1980; Posner, Snyder, & Davidson, 1980): The Posner Task is a spatial cueing paradigm that measures attentional engagement toward and disengagement from certain visual cues. The stimuli for this task will be modified to include a set of disgust, happy, and neutral faces. The task will consist of 360 trials. During each trial, the participant will see a fixation cross. On each trial, a face (disgust, happy, or neutral) will appear within either the top or bottom half of the screen (the other half of the screen will remain blank) and then disappear. Then, a probe (the letter "E" or "F") will appear in the top or bottom half of the screen. The participant will be instructed to identify the letter as quickly and accurately as possible by clicking the left or right mouse button (left for "E", right for "F"). Upon responding, the next trial will commence.

For valid trials, the probe will appear in the position previously occupied by the face stimulus, whereas for invalid trials, the probe will appear in the empty half of the screen. Response latencies for valid and invalid trials will reflect the participant's attentional engagement towards threat and disengagement from threat, respectively, and will be used to calculate attentional bias scores for threat cues.

Trust Game: The participant will be told that he will be playing the Trust Game with another player in a different room, and that both players will be allocated a sum of 10 game dollars to start the game. The participant will be told that he will take the role of Player 1. The instructions for the game will be as follows: Player 1 will have the opportunity to transfer all, some, or none of his 10 game dollars to Player 2, the sum given by Player 1 will be tripled, and Player 2 will have to choose to return some, all, or none of his game dollars to Player 1. The role of Player 2 will be played by a member of the study staff. The participant will play the Trust Game twice. The amount of money given by the participant is recorded and represents a measure of "trust". Three game dollars will equal \$1. The subject will be paid the value of this amount in dollars.

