Prior to analysis, all major variables will be screened for inconsistent or abnormal values, and continuous measures assessed for skewness and outliers. Variable distributions will be examined and transformations made when distributions are skewed or otherwise violate analytic assumptions. Linear regression models will be used, and in all models, the effect of diagnosis will be based not on the global (type III) effect, but on the specific pair-wise comparison of interest: BDD vs. Healthy Controls. Analyses will be conducted using SAS v9.4 (SAS Institute, Cary, NC), and all models will employ a two-sided alpha=0.05 to determine significance.

Aim 1 Analyses:

The primary outcomes will be the Emotion Recognition Task total score and the Trust Game "back transfer" amount. Two sets of outcome scores will be obtained for each subject - one during placebo and the other during oxytocin administration. To test Hypothesis 1a, we will regress placebo outcome scores against diagnosis. To test Hypothesis 1b, we will regress oxytocin outcome scores against diagnosis, and will control for the placebo outcome score. If we find significant differences in oxytocin Emotion Recognition Task total score by diagnosis, we will further examine the 3 Emotion Recognition Task valence categories (positive, negative, neutral) as exploratory outcomes.

Aim 2 Analyses:

Secondary outcomes include the Posner Task difference score for disengagement response latencies between disgust vs. neutral faces, and the Interpretation Questionnaire total score. Mirroring the analyses for the primary aim, we will test Hypothesis 2a by regressing the placebo secondary outcome scores against diagnosis, and will test Hypothesis 2b by regressing the oxytocin secondary outcome scores against diagnosis, controlling for the placebo secondary outcome scores.

Exploratory Analyses:

Exploratory moderators include the BDD-YBOCS total score, YBOCS total score, LSAS total score, BFNE total score, ECR Anxiety subscale mean, ECR Avoidance subscale mean, and IPSM total score. To test the moderation effects, we will enter each moderator (one at a time) into each of the aforementioned linear regression models along with a covariate representing the interaction between the moderator and diagnosis (the term of interest). We will examine moderation of each pair-wise comparison separately.

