For all analyses, we will include concomitant medication use as a covariate, in order to control for the effect of concomitant medications on study results. We will also compare participants who are taking psychotropic medications from participants who are not, on

demographic and clinical variables, to ensure there are no systematic differences between these groups.

Power and Sample Size:

Given the novelty of our approach, no background data on the effects of oxytocin in BDD exist to inform the power calculation. Therefore, the proposed sample size of 40 participants (20 per group) was chosen based on feasibility. With 20 participants per group and a two-sided alpha=0.05, for our primary pair-wise comparison (BDD vs. healthy controls) of the mean within-subject difference (oxytocin vs. placebo) in Emotion Recognition Task total score and Trust Game "back transfer" amount, we will have 81% power to detect a moderate effect size of $f=0.23$.

VII. Risks and Discomforts

Oxytocin-Related Risks and Side Effects:

Between 1990 and 2010, there have been 38 controlled studies involving intranasal delivery of oxytocin (MacDonald et al., 2011). A total of 1,529 participants have received intranasal oxytocin or placebo, and nine studies have included participants (N=182) who had a developmental, medical, or mental health disorder. The dosage of oxytocin has typically been a single dose ranging from 20 international units (IU) to 40 IU. Out of the 1,529 participants who have received intranasal oxytocin or placebo, 279 (18%) reported mild side-effects (MacDonald et al., 2011). The most common side-effect was a feeling of calmness, but this did not differ between those who received oxytocin or placebo. A recent review of studies using intranasal oxytocin supported the short-term use of oxytocin, demonstrating that oxytocin produced minimal side-effects, no detectable differences in side-effects between oxytocin or placebo recipients, no subjective changes in recipients, and is equally safe to use with vulnerable populations as with healthy adults (MacDonald et al., 2011). The proposed study intends to use a single 24 IU dose of intranasal oxytocin, which has been the most commonly used dose in previous trials (25 out of 38 studies).

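### The Trust Game primary outcome is defined as the participant's transfer in the task description but named as an undefined 'back transfer' in the analysis and power sections

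*Combined protocol and SAP*

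**What the plan says.** The Trust Game entry under Tasks in Section V casts the participant as Player 1, who may send any part of 10 game dollars. The sum sent is tripled. Then "Player 2 will have to choose to return some, all, or none of his game dollars to Player 1". On who that is: "The role of Player 2 will be played by a member of the study staff". On what is measured: "The amount of money given by the participant is recorded and represents a measure of 'trust". No other Trust Game quantity is described as an outcome measure.

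Section VI, Aim 1 Analyses, uses a different name: "The primary outcomes will be the Emotion Recognition Task total score and the Trust Game 'back transfer' amount". The Power and Sample Size paragraph repeats it: "Trust Game 'back transfer' amount, we will have 81% power". The term appears in those two places only and is not defined in either.

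On the number of plays, the Tasks introduction says "The following tasks will be administered at each study visit approximately 45 minutes after drug administration", the Trust Game entry says "The participant will play the Trust Game twice", and Aim 1 Analyses says "Two sets of outcome scores will be obtained for each subject - one during placebo and the other during oxytocin administration".

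**The concern.** Hypotheses 1a and 1b concern how participants perform. An analyst who follows Section VI literally would take the return made by a staff member as the outcome. Whether that says anything about participants' trust depends on how the staff member decides the return, and the plan does not say.

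There is also a selection risk. With two candidate variables for one primary outcome, the choice could be made after the results are known.

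A smaller gap sits beside this. If the game is played twice at each visit, a rule is needed to reduce two plays to one score per drug condition, and none is given.

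**Working it through.** **The plan's own figure.** Section VI gives 20 per group, two-sided alpha 0.05, f = 0.23 and 81% power. For a test of the group-by-condition interaction with two measurements per person, the noncentrality is N × m × f² / (1 − ρ). The plan gives no within-person correlation; assuming ρ = 0.5, this is 40 × 2 × 0.0529 / 0.5 = 8.464 on 1 and 38 degrees of freedom, and power is 80.9%. The stated figure is therefore reproduced under that assumption. Across assumed ρ of 0, 0.3 and 0.7, power is 51.8%, 66.9% and 95.5%. Because f is standardised, changing the outcome's name does not alter this arithmetic, only the variable to which f refers.

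**The sections side by side.**

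| Item | Section V, Trust Game | Section VI, Aim 1 and Power |
|---|---|---|
| Outcome | Amount given by the participant | *Back transfer* amount |
| Who decides it | Player 1, the participant | Player 2, a staff member, if read literally |
| Range or rule | 0 to 10 game dollars | Not stated |

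No section gives the participant the Player 2 role, so the two descriptions cannot refer to the same quantity as written.

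**What the literal reading would cost.** Let A be the amount given and s the share of the tripled sum returned. Then back transfer = 3 × s × A. If s is constant, the outcome is A multiplied by a constant (1.5 × A at s = 50%). The Hypothesis 1b covariate is rescaled in the same way, so the t statistics are unchanged. At s = 0 the outcome is constant and cannot be tested. If s varies from play to play, noise is added.

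Simulation: 20,000 trials per setting, 20 per group, two-sided alpha 0.05. The documents give no Trust Game mean or SD, so these inputs are assumptions:
- A has mean 5 and SD 2.5, rounded and limited to 0–10, with within-person correlation 0.5.
- Hypothesis 1a: group shift of −2.3 on placebo; placebo score regressed on diagnosis.
- Hypothesis 1b: group shift of +2.1 on oxytocin only; oxytocin score regressed on diagnosis and placebo score.
- The concomitant-medication covariate is omitted.

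| Outcome analysed | Correlation with A | Power, 1a | Power, 1b |
|---|---|---|---|
| Amount given | – | 80% | 82% |
| Return, fixed 50% share | 1.00 | 80% | 82% |
| Share varying 40–60% | 0.96 | 78% | 76% |
| Share varying 25–75% | 0.83 | 68% | 55% |
| Share varying 0–100% | 0.60 | 45% | 27% |
| Return unrelated to A | 0.00 | 5% | 5% |

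Repeat runs of the fixed- and varying-share cases agree to about one percentage point.

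Section V says both players start with 10 game dollars, so Player 2's pot could instead be 10 + 3 × A. For the three varying-share rows, power is then about 75%/70%, 53%/39% and 25%/17%. A fixed share again loses nothing.

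**Possible bias.** Section IV (Treatment Assignment Procedures) describes blinding to drug condition only and does not say whether Player 2 knows the diagnosis. If Player 2 did know, and average shares were 45% versus 50% with no true difference, the Hypothesis 1a false-positive rate would rise from 5% to about 10%. At 40% versus 50% it would be about 27% (21–29%, depending on how variable the share is).

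**Plays per visit.** If the tripled 30 game dollars is the most that can come back, two plays pay at most 30 × 2 / 3 = $20 and four plays 30 × 4 / 3 = $40. Section VIII caps Trust Game earnings at $20. This fits one play per visit if the cap covers the whole study, and two per visit if it applies to each visit. The hourly payment, (2.5 + 2 + 2) × $15 = $97.50, shows that the $100 maximum is study-wide. It does not settle the scope of the $20 cap.

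**The case against.** The most likely explanation is a labelling slip. Section V says plainly which quantity is recorded and what it stands for, no section describes Player 2's return as an outcome, and the hypotheses are about participants. The simulated losses come from invented means, correlations and share ranges, and the form of the return is itself uncertain. The bias case needs a Player 2 who knows the diagnosis, treats the groups differently, and whose return is then analysed; the documents establish none of these. The plays-per-visit question is a separate and lesser matter, and may need no combining rule at all.

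Most of this is fair. The percentages illustrate the problem rather than measure it, and the bias case is purely conditional. But a probable slip is not a resolved one. The undefined term stands in both places that fix the primary outcome, and nothing in the documents says which reading governs. The alternative pot makes the dilution worse, so it does not help the plan.

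**Conclusion.** The concern holds. Sections V and VI give conflicting definitions of one of the two primary outcomes, and the literal Section VI reading substitutes staff behaviour for participant trust. This conclusion needs no simulation.

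If the literal reading were followed, the cost would range from nothing (fixed share) to complete loss of information (return unrelated to the amount given). The documents do not show which case applies. The intermediate figures rest on the assumed distributions. The 81% power statement is not challenged on this point. The ambiguity must be settled before analysis because it leaves open which variable the primary test uses. The plays-per-visit point is a clarification and would not carry this weight alone.

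**What to change.** In Section VI, under both Aim 1 Analyses and Power and Sample Size, replace the *back transfer* label with the amount given by the participant as Player 1 (0 to 10 game dollars), matching Section V. If the sponsor does intend Player 2's return, Sections V and VI must instead define it, state the return rule and explain how it measures participants' trust.

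Add one sentence stating whether the game is played once or twice per visit and, if twice, how the plays become one score per drug condition (for example, their mean).

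Optionally, pre-set Player 2's return as the same share of the tripled sum for every participant and visit, so that feedback from an earlier play cannot differ by group. The inconsistency can be resolved without this.

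The required change is wording only, and the amount given is already recorded. The optional rule is a small change to staff procedure, with no added visits or staff.

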Given that oxytocin is involved in the regulation of a variety of dimensions of social cognition and behavior, including emotion recognition and social information processing, there are direct implications regarding its role in the development of such deficits among individuals BDD in particular. Individuals with BDD display deficits in social cognition, as they are convinced that their appearance is flawed, and that people may be staring and laughing at their physical flaws. Experiments have shown that BDD is associated with selective attentional biases to imagined flaws in one's own face and to corresponding regions in unfamiliar others' faces (e.g., Grochowski, Kleim, & Heinrichs, 2012). Moreover, research has shown that individuals with BDD incorrectly interpret faces showing neutral emotional expressions as contemptuous and angry (Buhlmann, Etcoff, & Wilhelm, 2006). Despite these obvious problems with regard to social cognition, no studies have yet examined the effect of oxytocin in BDD. The current study therefore aims to investigate the effect of oxytocin administration on modifying core social cognitive impairments associated with BDD. This study has major public health significance, given the prevalence of OC spectrum disorders and the need to investigate more parsimonious treatments.

II. Specific Aims

Primary Aim 1: To examine differential effects of oxytocin on social cognitive deficits during an emotion recognition task and trust game by diagnosis.

Hypothesis 1a: Individuals with BDD will exhibit poor performance on the emotion recognition task and trust game, compared to healthy controls.

Hypothesis 1b: The effects of oxytocin vs. placebo on the emotion recognition task and trust game will be greater for individuals with BDD than for healthy controls.

Secondary Aim 2: To examine the effect of oxytocin on cognitive biases (attentional and interpretive biases) associated with BDD.

Hypothesis 2a: Individuals with BDD (compared to healthy controls) will exhibit the following cognitive biases: attentional bias (difficulty disengaging from threat cues, as measured by a spatial cueing paradigm), and negative interpretive bias (as measured by an interpretation questionnaire).

Hypothesis 2b: For individuals with BDD (compared to healthy controls), oxytocin will attenuate these biases compared to placebo.

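### Hypotheses 1b and 2b, and the power statement, concern the oxytocin-minus-placebo difference, but the planned test is the placebo-adjusted oxytocin score, whose diagnosis coefficient also carries part of any placebo gap between the groups

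*Combined protocol and SAP*

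**What the plan says.** **Hypotheses (section II, Specific Aims).** Hypothesis 1b reads: "The effects of oxytocin vs. placebo on the emotion recognition task and trust game will be greater for individuals with BDD" than for controls. Hypothesis 2b says that, in BDD relative to controls, "oxytocin will attenuate these biases compared to placebo". Both are drug-by-diagnosis questions. Hypothesis 1a predicts a group gap: "Individuals with BDD will exhibit poor performance on the emotion recognition task and trust game, compared to healthy controls". Hypothesis 2a does the same for the biases: "Individuals with BDD (compared to healthy controls) will exhibit the following cognitive biases".

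**Outcomes and tests (section VI, Aim 1 and Aim 2 Analyses).** "The primary outcomes will be the Emotion Recognition Task total score and the Trust Game" back-transfer amount. For the group gap: "To test Hypothesis 1a, we will regress placebo outcome scores against diagnosis". For the drug question: "To test Hypothesis 1b, we will regress oxytocin outcome scores against diagnosis, and will control for the placebo outcome score". Aim 2 uses the same pair of models for the "Posner Task difference score for disengagement response latencies between disgust vs. neutral faces" and the Interpretation Questionnaire total.

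**Covariate and power (section VI).** Concomitant medication use enters every model. The Power and Sample Size paragraph claims 81% power at f = 0.23, with 20 per group and two-sided alpha 0.05, for the group comparison of the mean within-subject oxytocin-placebo difference.

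**Randomisation (section IV, Treatment Assignment Procedures).** Only the order of the two sprays is randomised.

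**The concern.** The hypotheses and the power statement agree with each other, but the named test does not match them. The planned model asks whether a BDD participant and a control with the same placebo score differ on oxytocin. The hypotheses ask whether the change from placebo to oxytocin differs between the groups. The two questions coincide when the groups have the same placebo mean, or when the slope is 1. Adjusting for a baseline is usually harmless because randomisation equalises its mean across groups. Here the groups are diagnostic, the covariate is the other crossover condition, and the trial's own hypotheses predict that the groups differ on it.

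The mismatch affects both primary and both secondary outcomes. It also carries forward: the exploratory emotion-category analyses are triggered by a significant result from this model, and the moderator analyses are built on the same regressions.

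**Working it through.** **1. The plan's own figure.** Inputs from Power and Sample Size: N = 40, two conditions, f = 0.23, alpha 0.05 two-sided. The within-person correlation rho is not stated. For a group-by-condition interaction, lambda = f^2 x N x 2 / (1 - rho). At rho = 0.5 this is 0.0529 x 80 / 0.5 = 8.464; with F(1, 38), power is 80.9%. The 81% is therefore reproduced for the difference test at rho 0.5 with no covariate. At rho 0.3 and 0.7 the same f gives 66.9% and 95.5%. At rho 0.5 the effect is a between-group difference in change of 0.92 SD.

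**2. The identity.** Use the same participants and covariates throughout.
- Planned model: oxytocin = c x diagnosis + b x placebo + covariates.
- Model for 1a or 2a: placebo = g x diagnosis + covariates.
- Dropping placebo from the first model gives a diagnosis coefficient of c + b x g.
- The regression of oxytocin minus placebo therefore has coefficient d = c + b x g - g.
- Hence c = d + (1 - b) x g.

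This is exact in any data set. Adding the medication covariate to all the models does not remove the extra term.

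**3. Direction, for a score where higher is better.**
- BDD worse on placebo (g < 0), b < 1: the shift is negative and hides a greater BDD benefit.
- BDD better on placebo (g > 0), b < 1: the shift falsely favours BDD.
- g = 0 or b = 1: no shift.
- b > 1: the directions reverse.

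If a secondary score is coded so that higher means more bias, a BDD deficit gives a positive shift, which again masks benefit.

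**4. Illustrative size.** Assumed, not in the documents: normal scores, SD 1 in both conditions (so the expected slope is rho), 20 per group, 10 of 20 BDD participants and no controls medicated, medication covariate included, BDD worse on placebo. Entries are planned v difference test; 40,000 simulated trials per setting.

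| Gap (SD) | rho | Shift (1 - rho) x gap | Rejection, no drug effect | Power, 0.92 SD effect in BDD only |
|---|---|---|---|---|
| 0.3 | 0.8 | 0.06 | 6% v 5% | 94.1% v 95.5% |
| 0.8 | 0.9 | 0.08 | 7% v 5% | 99.4% v 99.9% |
| 0.5 | 0.5 | 0.25 | 11% v 5% | 47% v 64% |
| 0.8 | 0.7 | 0.24 | 12% v 5% | 61% v 85% |
| 0.8 | 0.5 | 0.40 | 19% v 5% | about 30% v 64% |

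Without the covariate, the last power entry is 40% v 81%. The drop from 81% to 64% for the difference test thus comes from the assumed medication split, not from the choice of test.

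The near-equal power at high rho is saturation. At rho 0.9 the change has SD sqrt(2 x 0.1) = 0.447, so 0.92 raw SD is 2.06 SDs of change. Holding the effect at 0.92 SD of the change score, gap 0.8 and rho 0.9 gives about 44% v 64% with the covariate. Without it, at gap 0.8, the planned test has 35%, 39%, 46% and 58% power at rho 0.3, 0.5, 0.7 and 0.9, against 81%.

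**5. Other directions.** With BDD 0.8 SD better on placebo, rho 0.5 and no drug effect, the planned test falsely favours BDD in about 19% of trials. With BDD 0.8 SD worse, rho 0.9 and the oxytocin SD 1.3 times the placebo SD, the slope is 0.9 x 1.3 = 1.17 and the shift is (1 - 1.17) x (-0.8) = +0.14 SD; about 8% of trials falsely favour BDD.

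**The case against.** **The planned model is legitimate and can be more powerful.** This stands in part. With no placebo gap both tests target the same quantity and the planned one has more power: 75% v 64% at rho 0.5 with the covariate, 90% v 81% without. It keeps an advantage up to a gap of about 0.2 SD. That advantage exists only where 1a and 2a are false or the gap is small.

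**Nothing is lost.** True: the difference estimate can be recovered from the planned 1a and 1b fits. But the plan asks for neither that estimate nor its test, and choosing between the models after unblinding would be post hoc.

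**The difference test has its own weakness.** True near a score ceiling. Assume a maximum of 24, an uncapped control mean of 22, SD 3, gap 0.8 SD, rho 0.5 and the same 0.8 SD effect in both groups. The difference test then declares a greater BDD effect in 10.0% of trials with the covariate, against a nominal 2.5%. This falls to about 5% at a control mean of 20 and 3% at 18. The 24 is itself an assumption: the task description gives that range per questionnaire (self- and other-referent), so a combined total could reach 48.

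**Stronger readings that the documents do not support.** A reader might infer that the planned test always works against BDD, or can hardly ever favour it falsely. That fails if BDD is better on placebo, or if the slope exceeds 1; 1a is a prediction still to be tested. A reader might also infer that masking is established for all four outcomes. It is not. The Trust Game description records what the participant gives, while the analysis section names the back transfer, so no direction can be assigned. For the Posner score and the Interpretation Questionnaire total, the coding direction is not given.

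**Conclusion.** The mismatch is certain and covers all four outcomes: the test named for 1b and 2b does not estimate the quantity hypothesised and powered, and no other part of the plan supplies that test. The identity is also certain. Masking of a greater BDD benefit is conditional on BDD being worse on placebo and a slope below 1. The first is what 1a and 2a predict; the second is the ordinary case, since with equal SDs the slope is the within-group correlation.

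The size is not known. The documents give no gap, SD, correlation or medication share, and the illustrations run from negligible to large. The 19% should not be read as this trial's error rate: it is the rate for one assumed setting, when the planned coefficient is read as a test of the difference in drug effect. The point should be settled before the data are unblinded, because it concerns the main drug hypothesis.

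**What to change.** In the Aim 1 and Aim 2 Analyses, make the primary test of 1b and 2b the regression of each participant's oxytocin-minus-placebo difference on diagnosis, with the planned medication covariate and spray order. Keep the placebo-adjusted model as a sensitivity analysis.

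Order is worth including. With an assumed visit effect of 0.5 SD (gap 0.8 SD, rho 0.5, 0.92 SD effect), the difference test has 64% power with it and 54% without.

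An equivalent mixed model takes the drug x diagnosis term, with drug, diagnosis, period, a participant random effect, and both the medication main effect and drug x medication. Both medication terms are needed. In one check data set, drug x diagnosis was 0.83 with both and 0.77 when the main effect was left out; the difference regression gave 0.83. A medication main effect alone leaves drug x diagnosis unchanged.

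Report the share of Emotion Recognition Task scores at or near the maximum by group and spray, and state whether that maximum is 24 or 48. If many controls are there, add a sensitivity analysis that respects the bound.

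The cost is SAP wording, with the same data and software. The price is lower power if the placebo gap is below about 0.2 SD, and the ceiling sensitivity described above.
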